PREVUE v4, dd 12Dec2018

PREVUE; PlantaR flexion Exercise for Venous Ulcer Evaluation, a multi-centre, controlled, prospective, randomized feasibility trial

Version 4, dd 12 December 2018

Chief Investigator's Statement of Ownership and Content.

I, [name], confirm that this protocol is my work and is owned by me. The protocol conforms with standards outlined in the Declaration of Helsinki 1964.

Name (PRINT):___[name]_____

Signature:

Date: ____12 Decl 2018_____

RESEARCH PROTOCOL SUMMARY

TITLE:	PREVUE; PlantaR flexion Exercise for Venous leg UlcEr, a multi- centre, controlled, prospective, randomized feasibility trial
Short title:	PREVUE
IRAS number	222694
Device description	StepIt plantar flexion rocker pedal device. CE-marked and licensed medical device. To be used in this study for indicated purpose, namely plantar flexion exercise.
Study design	Single centre, controlled, prospective randomized feasibility trial
Primary objective	To assess the feasibility of conducting a full RCT in the future - Participants' compliance to StepIt exercise regime
	 Recruitment and attrition rates, willingness of patients to be randomised, response rates to questionnaires, and degrees of missing data Testing of eligibility criteria and ability/willingness of clinical staff to partake in recruitment of participants Adequacy of duration of follow-up (e.g. in relation to VLU healing)
Secondary objectives	To determine the acceptability and efficacy of the step-it pedal as an adjuvant therapy for VLU at 6 and 12 weeks post-baseline - Healing rate (ulcer size, PUSH score) - Ankle motion range - Patient mobility score - VLU-related quality of life score - VLU-related pain - Patient feedback on use of the device
Patient population	A total of 28 participants, over the age of eighteen, with venous leg ulcers and treated either in hospital or at home by the community nursing team. Participants must have the capacity to provide informed written consent and complete patient reported outcome measures. Participants are recruited from the local community nursing caseload and identified in hospital clinics. - 12 Patient will receive treatment as usual (TaU) - 12 Patients will receive TaU plus StepIt exercise programme intervention

	Randomisation will be stratified for ulcer size, with cut-off PUSH
	score of up to 8, and 9 and above.
Sponsor	Cumbria Partnership NHS Foundation Trust
Manufactures O foundan	Charalle Coreboure A.D.
Manufacturer & funder	StepIt System AB,

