Participants will be randomised to either the control group (standard care) or the intervention group (standard care plus use of a StepIt pedal) for 12 weeks or until ulcer healing has taken place. Patients in both groups will be given the usual leg ulcer information leaflet, but those in the intervention group will be issued with a StepIt Pedal to use daily for foot and ankle exercises. These exercises consist of resisted plantar flexion while seated, performed 2 times daily in the pattern of: 1 minute exercise / 1 minute rest, 10 times (participants may alternate legs as an alternative to merely resting both legs for 1 minute). The participants will be asked to keep an exercise diary to record their activity. At their discharge visits participants are asked to provide their opinion on trial participation. All participants will have demographic data obtained and the following base line measures (table 2):

- VLU size measured with Convatec grid tool
- PUSH score (size and characteristics)
- Mobility score
- Ankle range of motion using a goniometer
- Visual analogue pain score
- Quality of life assessment using the Charing Cross Venous Ulcer Questionnaire

Table 3. Baseline measures

Weeks	0	2	4	6#	8	10	12#
Ulcer size and PUSH score	Х			Χ			Χ
Mobility score	Χ			Х			Χ
Ankle range of motion	Χ			Х			Χ
Visual analogue pain score	Χ			Χ			Χ
Charing Cross Venous Ulcer Questionnaire	Х			Х			Χ

Allowed to be up to 2 weeks early or late

The Pressure Ulcer Scale for Healing (PUSH) tool, see Appendix 1 is a standardised method of assessing and monitoring the severity and healing of both pressure ulcers and venous leg ulcers (Stotts et al, 2001; Ratliff & Rodeheaver 2005). Concerns have been raised regarding the criterion validity and intra-rater reliability of the tool (Pillen et al 2009) however in the absence of other valid tools it provides a comprehensive parallel assessment of the ulcer along with measuring size alone.

A mobility measure will be taken using a life space questionnaire, see Appendix 1 (Stalvey *et al* 1999). This is a tool that has demonstrated reliability and construct and criterion validity in establishing the spatial extent of an older person's mobility within their home setting. There are other versions (Peel *et al* 2005) that additionally measure the use of aids and equipment however this is not of particular interest within the study, hence the simpler version will be used.

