A recent review of specific health related quality of life instruments for venous leg ulcers favours the Charing Cross Venous Leg Ulcer Questionnaire (appendix 2) (Smith *et al* 2010) above others such as the Hyland for its disease specific psychometric characteristics (Gonzalez & Verdu 2011).

During the recruitment process the research team acts as a contact point and coordinator for patients requiring information and support. If concerns are raised on participants (mental) wellbeing based on the home visits or outcome of the assessments, referral of patients/families on to other professional agencies will be done as appropriate and according to the Trust guideline.

5.4 **Follow-up**

Patients are in the study until the VLU is healed or for the maximum period of 12 weeks. The patient will be followed up as they would in normal clinical practice. The community nurse will redress the VLU as per routine care, and will conduct the measurement of the VLU (grid measurement and PUSH score). The researcher will visit the patient at baseline, week 6 and week 12 of study participation to randomise the patient, hand out the StepIt pedal, measure ankle range of motion and conduct the questionnaires.

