6.3 Early withdrawal of subjects

Patients have the right to withdraw from the trial at any time and without giving any reason. If a patient withdraws from the trial, any and all information gathered prior to the withdrawal will be excluded in the analysis, no further data collection will occur. If a patient does not attend a planned follow-up appointment then two more attempts will be made to contact the patient regarding the study. If still no contact can be made then the patient is deemed lost to follow-up and any collected study data will be retained.

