8.3 Secondary outcome statistics

To evaluate the effect of the StepIt exercises on VLU healing data from the control group will be compared with data from the StepIt group. The StepIt exercise data will be stratified into different groups according to coherence to treatment.

Healing is defined by the following parameters:

- Ulcer size
- PUSH score
- Mobility score
- Ankle range of motion
- Visual analogue pain score
- Charing Cross Venous Ulcer Questionnaire

To assess the Ulcer size, PUSH score and visual analogue pain scores which are measured every 6 weeks, the average difference between time points will be calculated per group. To compare the groups, Mann-Whitney U-test will be applied.

To assess mobility score and ankle range of motion, the average differences between first and last visit will be calculated. The control and intervention group will be compared by applying Mann-Whitney U-test or unpaired t-test depending on the distribution of the data.

To measure patient-reported outcome measures on quality of life at first visit and final visit, the Mann-Whitney U-test will be performed. Data of the control and intervention group will be compared by applying the Mann-Whitney U-test.

Subject to sufficient data being available, Cox proportional hazards regression analysis will be conducted to investigate the role of StepIt and other covariates in VLU healing rates. Other

covariates include: VLU size and age at baseline, ankle motion range, patient age, patient mobility, absence/presence of co-morbidities.

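### Section 8.3 analyses mobility, ankle range and quality of life from first to last visit, which mixes follow-up lengths that depend on healing and leaves the week-6 objective unestimated

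*Protocol*

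**What the plan says.** The Research Protocol Summary words the secondary objective as "To determine the acceptability and efficacy of the step-it pedal as an adjuvant therapy for VLU at 6 and 12 weeks post-baseline". Ankle motion range, mobility and ulcer-related quality of life are in its list. Table 3 (section 5.3) schedules all three at weeks 0, 6 and 12, and a note on the two later visits reads "Allowed to be up to 2 weeks early or late".

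Section 8.3 fixes the analysis differently. For two outcomes: "To assess mobility score and ankle range of motion, the average differences between first and last visit will be calculated". For the third: "To measure patient-reported outcome measures on quality of life at first visit and final visit, the Mann-Whitney U-test will be performed". It gives no week-6 or week-12 comparison for any of the three. In the same section, ulcer size, PUSH score and pain are handled as differences between time points.

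Four other places determine when the last visit falls:

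- Section 5.3 sets the study period in both arms as "for 12 weeks or until ulcer healing has taken place".
- Section 5.4 says "Patients are in the study until the VLU is healed or for the maximum period of 12 weeks", and "The researcher will visit the patient at baseline, week 6 and week 12 of study participation".
- Section 6.3 says that after failed contact attempts "the patient is deemed lost to follow-up and any collected study data will be retained". For a patient who withdraws, it excludes everything collected.
- Appendix 1 places the mobility and quality-of-life questionnaires at baseline and 12 weeks only. It does not mention ankle range.

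**The concern.** A first-to-last change has a clear meaning only if the last visit falls at about the same time for everyone. Here it can fall at healing, at loss to follow-up or at week 12. Time on study therefore depends partly on healing, which the device is meant to speed. If ankle range or mobility improves with weeks of exercise, patients who heal early contribute a shorter exposure, and the StepIt change shrinks for that reason alone. The result is in general neither the 6-week nor the 12-week effect.

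This matters even in a feasibility trial. Section 8.2 counts favourable quality-of-life change and signs of effectiveness among the grounds for a larger trial. Section 5.5.1 makes the adequacy of the follow-up period a primary outcome, and separate week-6 and week-12 changes would inform it. Section 6.1 says the results will feed the power calculation of the definitive trial. A mean and SD over mixed durations would be a poor input for any of these three outcomes.

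**Working it through.** The plan states no figure for this derivation, so there is none to reproduce. The check compares the sections and then sizes the effect under stated assumptions.

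**1. Objective against analysis.** The Summary asks for effects at 6 and 12 weeks, and Table 3 collects the values. Section 8.3 uses only the first and last. For a patient who completes week 12, the week-6 value enters no efficacy comparison of these outcomes. The week-6 effect is therefore not estimated.

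**2. When the last visit falls.** With researcher visits at baseline, week 6 and week 12:

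- A completer's last visit is at week 12.
- A patient who heals between the two later visits and leaves may have week 6 as the last measurement. The protocol does not say whether these outcomes are measured at healing.
- A patient lost after week 6 keeps the week-6 value, which becomes the last.
- A patient who withdraws contributes nothing.

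With the 2-week allowance, the interval can run from 6 - 2 = 4 weeks to 12 + 2 = 14 weeks, a ratio of 14/4 = 3.5.

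**3. Size in the simplest case.** Let D be the true StepIt effect at week 12 and f the share of StepIt patients whose last visit is week 6. Assume a linear gain (so D/2 at week 6), no change in controls, and early leavers on the same course as the rest.

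First-to-last difference = (1 - f)D + f(D/2) = D(1 - f/2).

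| f (assumed) | Share of 12-week effect retained |
|---|---|
| 0.1 | 1 - 0.05 = 0.95 |
| 0.3 | 1 - 0.15 = 0.85 |
| 0.5 | 1 - 0.25 = 0.75 |

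**4. Dependence on linearity.** If the week-6 effect is a fraction r of the week-12 effect, the retained share is 1 - f(1 - r). At f = 0.3 this is 0.70 for r = 0, 0.85 for r = 0.5 and 1.00 for r = 1. An effect complete by week 6 would not be diluted.

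**5. When controls also improve.** Let C be the 12-week change common to both arms, and h_S and h_C the shares last seen at week 6 in the StepIt and control arms. Then

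first-to-last difference = (C + D)(1 - h_S/2) - C(1 - h_C/2).

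Take D = 5 units, h_S = 0.3 and h_C = 0.1, all assumed:

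- C = 0: 5 × 0.85 = 4.25
- C = 5: 10 × 0.85 - 5 × 0.95 = 3.75
- C = 10: 15 × 0.85 - 10 × 0.95 = 3.25

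The true week-12 effect is 5 and the week-6 effect 2.5 throughout. The estimate changes with the common trend and the exit rates, although the effect of the device does not.

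**The case against.** The best defence is that the last visit means week 12. Appendix 1 puts mobility and quality of life at baseline and 12 weeks, so for two of the three outcomes the analysis could be read as baseline to week 12. That reading is available, but Appendix 1 conflicts with Table 3, cannot hold for a patient who leaves at healing, omits ankle range, and would still leave week 6 unanalysed. It shows that the protocol is inconsistent. It does not settle the matter.

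Change to the end of participation is also a coherent on-treatment summary, and these are secondary outcomes. Both points are fair and limit the weight of the finding. It is still not the quantity that the Summary names.

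Several stronger readings are tempting and should not be drawn:

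- *The protocol's 30% attrition is f.* Section 6.1 uses it for withdrawal and loss to follow-up together. Withdrawn patients' data are excluded under section 6.3, and patients lost before week 6 have no week-6 value. Early healing, which attrition does not count, would add to f. So f is unknown.
- *A definite loss of power.* That needs a gain and an SD for these outcomes, and the documents give neither.
- *False positive results.* With equal weekly gains, an assumed 6 units by week 12, and 50% v 20% last seen at week 6, the expected difference is 6 × 0.75 - 6 × 0.90 = -0.9, against StepIt. In a simulation of that case (14 per arm, SD 5, both assumed) the test rejected in about 6% of runs, close to the nominal 5%.
- *A baseline-only patient scores zero.* The natural reading is that such a patient has no change value and is missing.
- *Week-6 values are wasted.* They still serve response rates and missing data, which are primary feasibility outcomes.

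**Conclusion.** The point holds as a mismatch within the protocol. Section 8.3 fixes an analysis for mobility, ankle range and quality of life that does not estimate the week-6 effect set by the Summary. It also estimates the week-12 effect only if nearly everyone is last seen at week 12. The exit-at-healing and loss-to-follow-up rules mean this cannot be assumed, and Appendix 1 adds a third, conflicting schedule. This is not a detail left to an analysis plan, because the protocol itself states the derivation.

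The size is unknown. Under linear gain and no control change, the estimate keeps 95% of the 12-week effect at f = 0.1 and 75% at f = 0.5. With few early exits, or an effect complete by week 6, dilution is small. What is at stake is the estimates and the planning inputs, not the error rate of a test. It should be corrected, but it does not threaten the primary feasibility objective.

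**What to change.** In section 8.3, replace the first-to-last derivation for all three outcomes with change from baseline at the nominal week-6 visit and, separately, at the nominal week-12 visit.

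- Preferably use one repeated-measures model with baseline as covariate, including every week-6 value and so those of patients who leave before week 12. A test at each visit is the simpler alternative.
- Report both differences with 95% intervals, and the number of patients per visit and arm.
- State how the week-12 values of patients who healed early are handled, for example by continued outcome assessment or a defined missing-data rule. Note that a simple week-12 comparison covers only patients still in follow-up.
- Reconcile the Summary, Table 3, section 8.3 and Appendix 1 on when these outcomes are measured and analysed.

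The cost is wording and a little more analysis, since Table 3 already schedules the values. Any continued assessment after healing would add visits. The downside is real: fewer patients contribute at week 12, and they are selected by healing. If StepIt speeds healing, a simple week-12 comparison loses its early healers. The model deals with that only under a missing-at-random assumption, which should be stated.

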9. DATA HANDLING AND MONITORING

Data arising from this study is confidential. Identifiable information can only be accessed by delegated members of the study team. Anyone in the research team who does not have a substantive contract with Cumbria Partnership NHS Trusts will need to apply for a letter of access via the NIHR research passport scheme.

Patient identifiable data will only be used within each respective Trust; pseudo-anonymised data are shared with the wider members of the study team. All identifiable data is stored on password protected NHS computer systems. Anonymised data will be shared and stored using security-enabled systems such as password-protection and encryption of e-mails and files. The requirements of the Data Protection Act and NHS Code of Confidentiality will be followed at all times. All researchers will be fully trained in NHS Confidentiality and GCP. Participants' GP practices will be informed that they are taking part in the study.

All paper data will be held in secure locked environments in the office of the Research & Development department in the Carleton Clinic, Carlisle, Cumbria Partnership. Data released (e.g. by publication) will contain no information that could lead to the identification of an individual participant. Upon completion of the study the site files will be archived for a period of 10 years in line with local archiving policy and procedures. Direct access to anonymised data only will be granted to authorised representatives from the sponsor, host institution and the regulatory authorities to permit trial-related monitoring, audits and inspections.

As this concerns a pilot study, the trial will be monitored by the in-house research team who will convene on a monthly basis. A trial steering committee will not be convened for this trial.

10. GOVERANCE OF STUDY

10.1 Approvals

This study will be conducted in compliance with the protocol approved by the Health Research Authority, National Research Ethics Service, and local Trust R&D Approval, and according to Good Clinical Practice standards including the Declaration of Helsinki (1964, Amended Oct 2013). No deviation from the protocol will be implemented without the prior review and approval of the aforementioned review bodies, except where it may be necessary to eliminate an immediate hazard to a research subject. In such case, the deviation will be reported according to policies and procedures

10.2 Sponsor & Indemnity

Cumbria Partnership NHS Trust is the sponsor of this study and therefore NHS indemnity applies for design, conduct and management of the study. StepIt Ltd has provided a grant for this study by means of provision of the StepIt pedals free of charge

Patients will not be given financial incentives for taking part in the study. Travel expenses are not offered in this study since patients are seen at their home by community nurses or hospital as part of their normal care pathway. Patients randomised to the intervention group will be provided the StepIt device free-of-charge for the duration of the trial.

11. PUBLICATION AND DATA-SHARING POLICY

The study will be registered on the Clinical Trials Gov website, in line with CONSORT guidelines on good practice in clinical research.

The results of this study will potentially be disseminated through:

- Peer-reviewed manuscript in scientific journal
- Conference paper
- Internal report

A summary of the main findings can be supplied to participants on request and this will be stated in the patient information leaflet

APPENDIX 1. TOOLS AND ASSESSMENTS

This appendix contains:

- The PUSH tool that will be used to assess each leg ulcer at base line and 2 weekly thereafter. (from Stotts et al, 2001)
- The mobility life space questionnaire that will be completed for each participant to confirm limited mobility at base line and at 12 weeks (from Stalvey et al 1999)
- The Charing Cross Venous Ulcer Questionnaire used to score VLU-related quality of life for each participant at baseline and at 12 weeks (from Hareendran et al, 2005)
- Visual analogue pain scale

NATIONAL
PRESSURE
ULCER
ADVISORY
PANEL

Pressure Ulcer Scale for Healing (PUSH) PUSH Tool 3.0

Patient Name	Patient ID#	
Ulcer Location	Date	

Directions:

Observe and measure the pressure ulcer. Categorize the ulcer with respect to surface area, exudate, and type of wound tissue. Record a sub-score for each of these ulcer characteristics. Add the sub-scores to obtain the total score. A comparison of total scores measured over time provides an indication of the improvement or deterioration in pressure ulcer healing.

LENGTH	0	1	2	3	4	5	Sub-score
X	0	< 0.3	0.3 – 0.6	0.7 – 1.0	1.1 – 2.0	2.1 – 3.0	
WIDTH		6	7	8	9	10	
(in cm²)		3.1 – 4.0	4.1 – 8.0	8.1 – 12.0	12.1 - 24.0	> 24.0	
EXUDATE	0	1	2	3			Sub-score
AMOUNT	None	Light	Moderate	Heavy			
TISSUE	0	1	2	3	4		Sub-score
TYPE	Closed	Epithelial Tissue	Granulation Tissue	Slough	Necrotic Tissue		
							TOTAL SCORE

Life Space Questionnaire

Interviewer: "I am interested in all the places that you have been within the last 2 weeks" [It is acknowledged that original paper states 'within the last 3 days']

1.	During the past 2 week where you sleep?	s have you been to other rooms of your home besides the r	oom
	1 =Yes	2=No	
2.	During the past 2 week your porch, patio, garag	s have you been to an area immediately outside your home ge?	, such as
	1 =Yes	2=No	
3.	During the past 2 week courtyard, garden, driv	s have you been to an area outside your home such as a yar eway?	rd,
	1 =Yes	2=No	
4.	During the past 2 week beyond your own prop	s have you been to places in your immediate neighbourhoo erty?	d but
	1 =Yes	2=No	
5.	During the past 2 week but within your town o	s have you been to places outside your immediate neighbor community?	urhood
	1 =Yes	2=No	
6.	During the past 2 week community?	s have you been to places outside your immediate town or	
	1 =Yes	2=No	
7.	During the past 2 week	s have you been to places outside of Cumbria?	
	1 =Yes	2=No	

Quality of life assessment: Charing Cross Venous Ulcer Questionnaire

I have pain from my ulcer:

None of the time	A little of the time	Some of the time	A good bit of the time	All of the time	
1	2	3	4	5	

1. Having an ulcer on my leg stops me from doing the following:

	None of the time	A little of the time	Some of the time	A good bit of the time	All of the time
a. Meeting friends and relatives	1	2	3	4	5
b. Going on holiday	1	2	3	4	5
c. Enjoying my hobbies	1	2	3	4	5
d. Using public transport	1	2	3	4	5

2. How TRUE or FALSE is each of the following statements for you when considering your leg ulcer?

	Definitely true	Mostly true	Don't know	Mostly false	Definitely false
a. My ulcer has slowed me down in general	5	4	3	2	1
b. My ulcer has put a strain on my personal relationships	5	4	3	2	1
c. The discharge from my ulcer is a problem	5	4	3	2	1
d. I spend a lot of time thinking about my ulcer	5	4	3	2	1
e. I am worried that my ulcer will never heal	5	4	3	2	1
f. I am fed up with the amount of time it takes to treat my ulcer	5	4	3	2	1

3. I am unhappy about the appearance of my legs because of the ulcer and/or dressings

No, definitely not	Occasionally	Often	All of the time	
1	2	3	4	

4. My leg ulcer prevents me from the following household duties:

	None of the time	A little of the time	Some of the time	A good bit of the time	All of the time
a. Cooking	1	2	3	4	5
b. Cleaning	1	2	3	4	5
c. Shopping	1	2	3	4	5
d. Gardening	1	2	3	4	5

5. I feel depressed because of my leg ulcer

Never	Occasionally	Often	Always	
1	2	3	4	

6. Please state how much of a problem to you the following factors are regarding the dressings for your leg

	A huge problem	A big problem	A moderate problem	A little problem	No problem
a. The bulkiness them	5	4	3	2	1
b. The appearance of them	5	4	3	2	1
c. They influence the clothes I wear	5	4	3	2	1

[figure not shown]
7. I have difficulty walking because of my leg ulcer

Never	Occasionally	Often	Always	
1	2	3	4	

[figure not shown]
Total score:

(A score of 100 is the worst possible situation)

Visual analogue Pain score:

[figure not shown]

